saturation of themes is reached. Participants will undergo informed consent prior to participating, and will be compensated 50RM for their time.

Upon making an informed decision using the SDM developed from the focus groups, those that choose methadone maintenance treatment (MMT) will initiate 5 mg of methadone, 3-4 months prior to release from prison. The dose will increase in 5 mg increments every 7 days (as tolerated) until the daily dose is escalated to at least 80 mg or optimal dose before the date of release. Patients prescribed MMT will receive medication daily in prison, and will receive their medications weekly in form of take-way dosing. MMT will be dispensed at the community research site. All participants will be maintained on medication-assisted treatment and will receive follow-up care for 6 months after release from prison.

After a baseline assessment, our research assistant (RA) would meet the participant at the prison on the day of release to undergo a brief assessment, urine testing and to introduce the patient to our community research site to ensure that s/he can find the site after release and take the participant home so that our research assistants can know where the person is living/residing. This process will also improve trust between the research staff and the participant. Thereafter, all participants will be seen monthly, where they will undergo urine screening and be assessed for alcohol and drug use using timeline follow-back (TLFB), appointments for HIV and/or TB, adherence to HIV and/or TB medications, assessments of legal, employment, family issues using the Lite version of the Addiction Severity Index (ASI), depressive symptoms, health-related quality of life (HRQoL), satisfaction with their treatment. They will also be assessed for diversion (and urine testing).

The primary outcome will be the proportion completing treatment for active or LTBI. Secondary analyses will compare Kaplan Meier curves using Cox proportion hazards and time to discontinuation. TB treatment adherence will also be measured using MEMS caps and analyzed as we have done previously in TB patients in Ukraine

Eligibility for Part C includes:

- 1) Meets inclusion for part A, if possible
- 2) Opioid dependence
- 3) Has LTBI or active TB disease (based on screening in Part A), or no TB
- 4) Returning to live in Kuala Lumpur/Klang Valley region (within 25 km of Kerinchi research site), if possible
- 5) ≤ 6 months before end of sentence

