Part A: New intakes from Kajang Prison will be recruited (80-120) per day. Mandatory HIV testing is done on all prisoners. HIV prevalence is 5%. All HIV+ prisoners upon entry will be approached for informed consent. For Part B, only prisoners who have >9 months (preferably 12 months) remaining on their prison sentence will be approached for recruitment. All subjects are expected to be Southeast Asians/Pacific Islanders. While women will represent only 10% of the sample, they will be included. The minimum age is 18 years of age, thus children 18-21 years old will be eligible for participation. Currently, only 2% of HIV+ prisoners are between 18-21 years. For part C, prisoners who have less than 90 days remaining on their prison sentence, but more than 90 days of TB treatment remaining will be approached for recruitment. They must be at least 18 years old, have latent TB infection defined by TST \geq 5mm (HIV+), or TST \geq 10mm (HIV-), return to live in Klang Valley (within 25 km of Kerinchi research site), and AST/ALT <5 X ULN.

Aim 2 will not include Human Subjects. Data analysis only.

6. Subject classification: Check off all classifications of subjects that will be specifically recruited for enrollment in the research project. Will subjects who may require additional safeguards or other considerations be enrolled in the study? If so, identify the population of subjects requiring special safeguards and provide a justification for their involvement.

 Children	 Healthy	 Fetal material, placenta, or dead fetus
 Non-English Speaking	 Prisoners	 Economically disadvantaged persons
 Decisionally Impaired	 Employees	 Pregnant women and/or fetuses
 Yale Students	 Females of childbearing potential	

NOTE: Is this research proposal designed to enroll children who are wards of the state as potential subjects? Yes No (If yes, see Instructions section VII #4 for further requirements)

7. Inclusion/Exclusion Criteria: What are the criteria used to determine subject inclusion or exclusion?

Inclusion and Exclusion Criteria:

1a: inclusion:

- Above 18 years old
- Malaysian Citizen
- Newly admitted (<2 days)
- Able to provide consent
- Absence of active TB within 2 years of enrollment

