Methadone: Methadone is the current standard of care for treating opioid use disorders in Malaysia, and will be provided as part of routine clinical care. The most concerning problem that we are likely to encounter is drug interactions with either TB medication (specifically rifampin) or HIV medications (for which there are many). All patients initiating TB or HIV medications AFTER being stabilized on MMT will be monitored daily for two weeks for symptoms of opioid withdrawal using the Clinical Opioid Withdrawal Scale (COWS). We anticipate, however, that most patients will start their TB medications before receiving OAT and precipitating withdrawal symptoms will be unlikely. For those already on OAT, MMT doses will be increased by 5mg per day for mild symptoms, 10 mg per day for moderate symptoms and 20 mg per day for severe withdrawal using the Clinical Opioid Withdrawal Scale (COWS).

Buprenorphine/Naloxone (BPN/NLX): BPN/NLX, also known by the name SUBOXONE, consists of a mixed medication of buprenorphine (BPN) and naloxone (NLX) in a 4:1 ratio by mass, respectively. BPN is a μ -opioid receptor partial agonist, which functions by partially activating opioid receptors and imitating its effects; however, BPN's effect plateaus, thus giving the user only a minimal effect. NLX is a μ -opioid receptor antagonist with slightly lower affinity to opioid receptors than buprenorphine. When administered in combination with BPN, it aids in further reducing the partial agonist effect of BPN, especially when such is injected. Together, they ameliorate the euphoric and sedative effects of opioids by binding and blocking opioid receptors to reduce cravings by inducing a less intense receptor activation. BPN/NLX is FDA approved to treat opioid use and alcohol use disorders, and is available for use under the tongue or on the inside of the cheek. BPN/NLX has sometimes been a preferred mode of MAT as it has a reduced potential for diversion or abuse, can be taken home for daily self-administration and has shown increased engagement and retention in community-based treatment. (Malta, et al., 2019). Additionally, The buprenorphine/naloxone combination tablet (BPN/NLX) was

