- c. Assessment of adverse consequences: Several different research staff members will assess subjects in both the MMT and IPT interventions. For those on MMT who receive either HAART or TB Treatment, we will monitor for symptoms of opioid withdrawal. Alternatively, we will monitor for overdose in these subjects, diversion or drug interactions with MMT. We would also monitor for breaches of confidentiality in PT subjects. An initial investigation would be undertaken and simultaneously reported to the IRB using standard university procedures.
- d. Confidentiality of research data: Breaches of confidentiality regarding research data are more difficult to detect. For that reason, we have in place a number of safeguards including double-locked doors, locked file cabinets, confidential and dedicated fax machine and double password-protected computers. In accordance with federal and university policy, all research personnel are compliant with HIPAA training. If any breach of data confidentiality were detected, we would use similarly detailed procedures for report to the PI and IRB simultaneously.
- e. Complications from MMT: In this study, we will monitor for adverse consequences in a standard way. First, drug interactions between buprenorphine and HIV antiretrovirals have not been extensively evaluated. Efavirenz and nevirapine have been associated with reductions in methadone levels, and precipitated clinical withdrawal. In cases where we can detect symptoms of opiate withdrawal, we will increase the methadone dose to treat the symptoms of withdrawal. [name] was the first clinician to report cases of opiate withdrawal among patients receiving HAART and methadone and is currently investigating other pharmacokinetic interactions between methadone and buprenorphine with antiretroviral drug interactions. Methadone may

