a. Describe how potential subjects will be identified.

AIM 1:

Part A: Recruitment will take place among all new prison intakes as noted above. Informed consent procedures will occur in our private room in the prison medical unit with a closed door but plexiglass window so that we can assure the prison staff that security regulations are not being breached. The risks and benefits of the study will be described. The risks are minimal and include phlebotomy of 30cc of blood (2 tbsp), chest radiograph (minimal radiation exposure) and expectoration of sputum.

Part B: Among those in Part A who have LTBI and who otherwise meet eligibility criteria, they will undergo informed consent in the private research room at the prison with a plexiglass door in a similar manner as done for Part A.

Part C: Among those in Part A who have LTBI or active TB, 6 months or less remaining in prison and who otherwise meet eligibility criteria, they will undergo informed consent in the private research room at the prison with a plexiglass door in a similar manner as done for Part A.

Participants in Parts A and B will NOT be compensated for ANY research activities while within the prison. This is done to avoid any real or perceived level of coercion. Participants in Part C, however, will receive mobile flip phones, with calling minutes added every month of follow-up. The mobile phones will be used to communicate with participants to facilitate scheduling follow-up appointments post-prison release. Participants who already have their own personal mobile phone prior to prison

release can use their personal devices and will still be offered to have minutes added to their phone each month. To thank participants for participating in our study they will be offered the option to keep the mobile phone at the end of the study or receive the monetary equivalent of the mobile phone (RM50 or ~16.67).

AIM 2: No human subjects will be used.

- b. Describe how potential subjects are contacted.

Subjects will be contacted in the prison and asked if they would like to learn more about the project.

- c. Who is recruiting potential subjects?

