Part A: New intakes from Kajang Prison will be recruited daily. Mandatory HIV testing is done on all prisoners. HIV prevalence is 5%. All prisoners that meet pre-screening eligibility and who are interested in participating in the study will be approached for informed consent. For Part B, only prisoners who have >6 months (preferably 12 months) remaining on their prison sentence will be approached for recruitment. For Part C, prisoners who have less than 6 months remaining on their prison sentence will be approached for treatment.

Subjects will be recruited by local research assistants.

4. Screening Procedures

- a. Will email or telephone correspondence be used to screen potential subjects for eligibility prior to the potential subject coming to the research office? Yes No
- b. If yes, identify below all health information to be collected as part of screening and check off any of the following HIPAA identifiers to be collected and retained by the research team during this screening process.

HEALTH INFORMATION TO BE COLLECTED:

HIPAA identifiers:

- Names
- All geographic subdivisions smaller than a State, including: street address, city, county, precinct, zip codes and their equivalent geocodes, except for the initial three digits of a zip code if, according to the current publicly-available data from the Bureau of the Census: (1) the geographic unit formed by combining all zip codes with the same three initial digits contains more than 20,000 people, and (2) the initial three digits of a zip code for all such geographic units containing 20,000 or fewer people is changed to 000.
- Telephone numbers
- Fax numbers
- E-mail addresses
- Social Security numbers
- Medical record numbers
- Health plan beneficiary numbers
- Account numbers
- All elements of dates (except year) for dates related to an individual, including: birth date, admission date, discharge date, date of death, all ages over 89 and all elements of dates (including year) indicative of such age, except that such ages and elements may be aggregated into a single category of age 90 or older
- Certificate/license numbers

- Vehicle identifiers and serial numbers, including license plate numbers
- Device identifiers and serial numbers
- Web Universal Resource Locators (URLs)
- Internet Protocol (IP) address numbers
- Biometric identifiers, including finger and voice prints
- Full face photographic images and any comparable images
- Any other unique identifying numbers, characteristics, or codes

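### Part C: the routine methadone schedule needs 105 days to reach 80 mg, so those who need that dose and start about 91–104 days before release leave prison on 70–75 mg; a conflicting 90-day recruitment window also needs aligning

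*Combined protocol and SAP*

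**What the plan says.** The schedule is in Section V, item 3 (Research Plan), Part C. Participants who choose methadone "will initiate 5 mg of methadone, 3-4 months prior to release from prison. The dose will increase in 5 mg increments every 7 days", if tolerated. The end point of titration is given next: steps go on "until the daily dose is escalated to at least 80 mg or optimal dose before the date of release". Medication is then dispensed weekly at the community site, with 6 months of follow-up care. The text does not say whether weekly steps continue after release.

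Two other places allow extra increases. Section V, item 9 (Risks, Methadone), covering TB or HIV drugs started after stabilization on methadone: "For those already on OAT, MMT doses will be increased by 5mg per day for mild symptoms, 10 mg per day for moderate symptoms", with a larger step for severe symptoms. Section V, item 11 (complications from MMT): "In cases where we can detect symptoms of opiate withdrawal, we will increase the methadone dose to treat the symptoms of withdrawal".

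The time-to-release window for Part C is stated in five places:

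- Section V, item 3, eligibility list: 6 months or less.
- Section V, item 7, 1c inclusion: 6 months or less.
- Section VII, item 3a: "who have LTBI or active TB, 6 months or less remaining in prison".
- Section VII, item 3c: "For Part C, prisoners who have less than 6 months remaining on their prison sentence".
- Section V, item 5 (Subject Population): "For part C, prisoners who have less than 90 days remaining on their prison sentence".

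The Subject Population paragraph also differs on Part B: "For Part B, only prisoners who have >9 months (preferably 12 months) remaining on their prison sentence". Sections V.3, V.7 and VII.3 use about 6 months for Part B.

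**The concern.** The plan sets a dose target and a deadline for it, and gives the starting dose, step size, interval and start window. These can be checked against each other, and the late end of the start window does not leave enough weeks for the steps. The recruitment window in the Subject Population section goes further: staff who followed it could hardly start methadone as early as the dosing text requires.

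What is at stake is the dose on leaving prison. The reference list (item 33) includes a Malaysian prison pilot whose title links methadone dose at release to retention in treatment. The plan also notes that rifapentine, rifampin, efavirenz and nevirapine may lower methadone exposure, so a need for higher doses is plausible in this population, though the documents do not quantify it.

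**Working it through.** **Inputs.** All are from Section V, item 3, Part C: start 5 mg; step 5 mg; interval 7 days; target 80 mg or more, or the optimal dose, before release; start 3 to 4 months before release. With a mean month of 30.44 days, 3 months = 91.3 days and 4 months = 121.8 days.

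**Time to 80 mg.** Steps = (80 − 5)/5 = 15. Days = 15 × 7 = 105, or 105/30.44 = 3.45 months.

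**Dose by start day.** Count the first dose as day 0 and release as day *d*. With no held week, dose on release day = 5 + 5 × floor(*d*/7). The day before release uses *d* − 1.

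| Start, days before release | Release day | Day before release |
|---|---|---|
| 89 | 65 mg | 65 mg |
| 91 | 70 mg | 65 mg |
| 92–97 | 70 mg | 70 mg |
| 98 | 75 mg | 70 mg |
| 99–104 | 75 mg | 75 mg |
| 105 | 80 mg | 75 mg |
| 106 | 80 mg | 80 mg |
| 112 | 85 mg | 80 mg |
| 120–122 | 90 mg | 90 mg |

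The target is therefore met from a 4-month start and missed from a 3-month start. Of the 32 whole-day starts from 91 to 122, 14 (91–104) give less than 80 mg on release day. If the dose must be in place before the release date, as the plan words it, 15 (91–105) fall short. These are counts of possible start days, not of participants.

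**Size of the shortfall against 80 mg.** 80 − 75 = 5 mg to 80 − 65 = 15 mg. If the weekly clock kept running after release, 80 mg would be reached 105 − *d* days later: 14 days for a start at 91, 1 day for a start at 104.

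**Held weeks.** Each week held for tolerability delays 80 mg by 7 days: day 112 with one, day 119 with two.

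**Sensitivity.** A calendar quarter can be 89–92 days. Read as 89 or 90 days, a 3-month start gives 65 mg.

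**The 90-day window.** At most 89 whole days remain, so floor(89/7) = 12 steps and 5 + 60 = 65 mg at most. A start 3 to 4 months out is essentially impossible.

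**Room for an earlier start.** Six months = 182.6 days. Starting at 112 days leaves 182.6 − 112 = 70.6 days, about 10 weeks, for consent, baseline and the decision aid. Compared with a 91-day start it is 112 − 91 = 21 days earlier.

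**The case against.** The strongest reply is that the target is clinical. It is met by the optimal dose, steps depend on tolerance, and methadone is described as routine care with daily observation by a methadone nurse. The midpoint of the start range, (91.3 + 121.8)/2 = about 106.5 days, already fits the schedule. The gap for late starters is one or two weekly steps in people seen at a community site, and nothing says titration stops at release. The pilot's title gives no dose threshold and concerns retention, and the body text available does not cite it.

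Much of this stands, and it limits the size of the point. It does not remove it. The optimal-dose alternative exempts only people who need less than 80 mg. Tolerance can only slow the steps. The withdrawal-driven increases respond to symptoms and are not a planned route to 80 mg, and Section V.9 expects withdrawal on starting TB drugs to be unlikely because most patients will start those first. Continued titration after release would be sensible, but the plan does not state it.

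Three stronger readings are tempting and are not supported:

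- **That the whole methadone arm is held to 65 mg.** This needs the 90-day window to be the operative rule. The eligibility list, the inclusion criteria and both recruitment paragraphs say about 6 months, and the paragraph with the 90-day figure also carries an out-of-line Part B figure. It looks like text that was not updated.
- **That 70–75 mg is a ceiling.** Sections V.9 and V.11 permit further increases for withdrawal.
- **That the Part C comparison of TB treatment completion is biased or underpowered as a result.** The documents show no link from this dose gap to that outcome, and no Part C power calculation depends on it.

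**Conclusion.** The point holds in limited form. The late part of the plan's start window cannot meet its release target on the routine schedule for participants who need 80 mg or more. For starts 91–104 days out they are on 70–75 mg on release day, or 65–75 mg the day before. Someone whose optimal dose exceeds 80 mg needs longer still: 90 mg takes 17 steps, or 119 days. This assumes a step exactly every 7 days, no withdrawal-driven increase and no held week; held weeks widen the gap. The documents give neither actual start times nor the share of people who need 80 mg or more, so the number affected could be anywhere from none to all of that subgroup.

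The conflict between the 90-day and 6-month windows is a separate inconsistency in current text and should be corrected. Both corrections are cheap and worth making; neither touches sample size, power or alpha.

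**What to change.** 1. **Section V, item 3, Part C.** Replace the 3-to-4-month start with a planned start at least 16 weeks (112 days) before expected release. This gives 80 mg before the release date and allows for about one held week: with a full week held, 80 mg falls on release day itself.
2. **Same section.** State that anyone who enters Part C too late for this may still start methadone, and that titration then continues at the community site after clinical assessment. The 112 days is thus a planning rule for methadone and not an eligibility limit, so late entrants and those who choose no OAT stay eligible.
3. **Section V, item 5.** Change the Part C window to 6 months or less. In the same paragraph, align the minimum TB treatment remaining and the latent-TB requirement with the current criteria in Sections V.3 and V.7, which also admit people with active TB or no TB. Align the Part B figure of more than 9 months with the 6-month criterion in Sections V.3, V.7 and VII.3.
4. **Data.** Record and report methadone dose at release, ideally with a note of whether it was judged optimal, since otherwise a dose below 80 mg cannot be interpreted.

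The cost is wording in two sections and one or two REDCap fields. Methadone participants who would have started at 3 months must be identified and consented about 3 weeks earlier, which the 6-month window allows. Late starters need one or more dose steps with clinical assessment after release, for which weekly dispensing gives a contact.
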